BASELINE VARIABLES

- Subject Demographics
- Medications and Procedures
- Diet and Exercise

PRE-TREATMENT OUTCOME ASSESSMENTS

- Body Mass Index (BMI)
 - Height (in)
 - Weight (kg)
- Circumference measurements: waist and hips
- Digital Photographs

TREATMENT ADMINISTRATION PHASE

TREATMENT ADMINISTRATION PROTOCOL

- The treatment administration phase of the study may commence on the same day as the pre-treatment measurements are recorded.
- The treatment administration phase will extend over four consecutive weeks.
- Each subject will receive eight total treatment administrations with the Erchonia® GVS across the consecutive four-week treatment administration phase; two treatment per week; each one at least two days apart.
- Each treatment will take place at the investigator's test site.
- The treatment administration protocol for each session is as follows:
 1. The subject enters the treatment administration room and lays comfortably on a treatment table.
 2. The subject is correctly fitted with the safety glasses.
 3. The center of the Erchonia GVS treatment head is positioned approximately 4 inches above the subject's abdomen. The GVS treatment head is aligned so that one set of the three central laser diodes is positioned over the left side of the abdomen, while the other set of three central diodes is positioned over the right side of the abdomen.
 4. The two adjustable outer arms of the Erchonia GVS are then positioned over the left and

- right flanks, respectively, at a distance of approximately 4 inches.
5. The Erchonia® GVS is activated for 30 minutes. Each laser beam will create a spiraling circle pattern that is totally random and independent from the others. These patterns overlap each other to guarantee total coverage within the target area (abdomen).
 6. The Erchonia® GVS treatment will run 30 continuous minutes and will stop once treatment time is at 0:00. Once the “Time Remaining” display reaches 0:00 the treatment is complete, and the laser lights and the laser indicator light will turn off.
 7. After the Erchonia® GVS is turned off, the subject removes the safety glasses and leaves the treatment administration room.

TREATMENT ADMINISTRATION RECORD

Following the completion of each treatment with the GVS laser, the investigator will record the following:

- Number of treatment administration
- Date
- Investigator signature
- Adverse event (if applicable).

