An adverse event (AE) or suspected adverse reaction is considered "serious" if, in the view of either the investigator or sponsor, it results in any of the following outcomes: death, a life-threatening adverse event, inpatient hospitalization or prolongation of existing hospitalization, a persistent or significant incapacity or substantial disruption of the ability to conduct normal life functions, or a congenital anomaly/birth defect. Important medical events that may not result in death, be life-threatening, or require hospitalization may be considered serious when, based upon appropriate medical judgment, they may jeopardize the subject and may require medical or surgical intervention to prevent one of the outcomes listed in this definition.

It is not anticipated that any SAE will occur from participation in this study.

UNANTICIPATED ADVERSE DEVICE EFFECT (UADE) DEFINITION

An unanticipated adverse device effect is defined as any serious adverse effect on health or safety, or any life-threatening problem or death caused by, or associated with, a device, if that effect, problem, or death was not previously identified in nature, severity, or degree of incidence

in the investigational plan, or any other unanticipated serious problem associated with a device that relates to the rights, safety, or welfare of subjects.”

CLASSIFICATION OF AN ADVERSE EVENT

A. Severity of Event

All AEs will be graded for severity by the study investigator according to the following grading system definitions.

- **Mild:** Event requires minimal or no treatment and does not interfere with the subject’s daily activities.
- **Moderate:** Event result in a low level of inconvenience or concern with the therapeutic measures. Moderate events may cause some interference with functioning.
- **Severe:** Event interrupts a subject’s usual daily activity and may require systemic drug therapy or other treatment. Severe events are usually potentially life-threatening or incapacitating.

B. Relationship to Study Intervention

All AEs will have their relationship to the study intervention assessed by the study investigator who examines and evaluates the subject based on temporal relationship and his/her professional clinical judgment. The degree of certainty about causality will be graded using the categories below. In a clinical trial, the study product must always be suspect.

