- **Definitely Related:** There is clear evidence to suggest a causal relationship, and other possible contributing factors can be ruled out. The clinical event occurs in a plausible time relationship to study capsule administration and cannot be explained by concurrent disease, medications, or other treatments.
- **Probably Related:** There is evidence to suggest a causal relationship, and the influence of other factors is unlikely. The clinical event occurs within a reasonable time after administration of the study capsule, is unlikely to be attributed to concurrent disease, medications, or other treatments.
- **Not Related:** The AE is completely independent of study capsule administration, and/or evidence exists that the event is definitely related to another etiology. The alternative, definitive etiology must be fully documented by the clinician.

C. Expectedness

The study investigator will be responsible for determining whether an AE is expected or unexpected.

An AE will be considered **unexpected** if the nature, severity, or frequency of the event is not consistent with the risk information previously described for the study intervention.

An AE will be considered **expected** if the nature, severity, or frequency of the event is consistent with the risk information previously described for the study intervention.

TIME PERIOD AND FREQUENCY FOR EVENT ASSESSMENT AND FOLLOW-UP

The occurrence of an AE or serious adverse event (SAE) may come to the attention of study

personnel during study visits and interviews of a study subject presenting for medical care, or upon review by a study monitor.

An **unsolicited AE** is defined as one that is reported without specific prompting or in response to a general question.

A **solicited AE** is one that is specifically solicited through asking a question regarding a specific potential AE.

Reporting and data collection for an AE will distinguish if a captured AE was unsolicited or solicited.

AEs will be collected throughout study duration.

REASONABLY ANTICIPATED AND POTENTIAL ADVERSE EVENTS

SAEs are not anticipated to occur in this clinical study.

There are no anticipated adverse events in this clinical study.

Potential adverse events that may feasibly occur from application of the Erchonia® GVS laser device include, but are not necessarily limited to skin irritation, discoloring, rash, indentations, or infection.

ADVERSE EVENT RECORDING

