All AEs that occur, including local and systemic reactions, not meeting the criteria for SAEs will be captured on the appropriate AE case report form (CRF). Information to be collected includes event description, time of onset, clinician's assessment of severity, relationship to study product (assessed only by those with the training and authority to make a diagnosis), corrective action taken, time of resolution/stabilization of the event and if the subject was withdrawn from the study because of the AE. Recording will be done in a concise manner using standard, acceptable medical terms.

All AEs occurring while on study must be documented appropriately regardless of relationship. All AEs will be followed to adequate resolution.

Any medical condition that is present at the time that the subject is screened will be considered as baseline and not reported as an AE. However, if the study subject's condition deteriorates at any time during the study, it will be recorded as an AE.

Changes in the severity of an AE will be documented to allow an assessment of the duration of the event at each level of severity to be performed. AEs characterized as intermittent require documentation of onset and duration of each episode.

The study investigator will record all reportable events with start dates occurring any time after informed consent is obtained until 7 (for non-serious AEs) or 30 days (for SAEs) after the last day of study participation.

Events will be followed for outcome information until resolution or stabilization.

ADVERSE EVENT REPORTING

Adverse Event Reporting Timeframes

The table below lists the minimum AE reporting requirements for study Investigators. Reporting of all safety events to the Sponsor will be completed through Investigator submission of the AE CRF and any applicable supporting documentation

Table 1: Investigator AE Reporting Requirements

Type of AE	Report to	Reporting Timeframe (from time of learning of event)
Adverse Event (AE)	IRB	Per IRB reporting requirements
	Sponsor	Within 10 working days
Serious Adverse Event (SAE)	Sponsor	Within 24 hours
	IRB	Per IRB reporting requirements
Device Deficiency	Sponsor	Within 48 hours
	IRB	If SAE occurs due to the device deficiency, within 24 hours of learning of the event and per IRB reporting requirements
Device Related AE/SAE	Sponsor	Within 24 hours

Unanticipated Adverse Device Effect (UADE) Reporting

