- Unexpected in terms of nature, severity, or frequency given (a) the research procedures that are described in the protocol-related documents, such as the Institutional Review Board (IRB)-approved research protocol and informed consent document; and (b) the characteristics of the subject population being studied;
- Related or possibly related to participation in the research (“possibly related” means there is a reasonable possibility that the incident, experience, or outcome may have been caused by the procedures involved in the research); and
- Suggests that the research places subjects or others at a greater risk of harm (including physical, psychological, economic, or social harm) than was previously known or recognized.

This definition could include an unanticipated adverse device effect, any serious adverse effect on health or safety or any life-threatening problem or death caused by, or associated with, a device, if that effect, problem, or death was not previously identified in nature, severity, or degree of incidence in the investigational plan, or any other unanticipated serious problem associated with a device that relates to the rights, safety, or welfare of subjects (21 CFR 812.3(s)).

PRIVACY AND CONFIDENTIALITY

REGULATORY, ETHICAL, AND STUDY OVERSIGHT CONSIDERATIONS

Informed Consent Process

An informed consent form (in written paper or in electronic format) describing in detail the study intervention, study procedures, and risks is given to each subject and written or electronically captured with identity verification documentation of informed consent is required prior to the subject starting any study activities, including study qualification evaluation. There are no other consent documents provided to subjects in this study.

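### The adverse-event causality scale names a study capsule instead of the laser and has no level for an event that the laser or another cause could plausibly explain

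*Combined protocol and SAP*

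**What the plan says.** The intervention is a laser. The Treatment Administration Protocol states: "Each subject will receive eight total treatment administrations with the Erchonia® GVS across the consecutive four-week treatment administration phase". No other study product is described.

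Under Classification of an Adverse Event, part B (Relationship to Study Intervention), the investigator judges every AE for its relationship to the intervention: "The degree of certainty about causality will be graded using the categories below". The next sentence sets the default stance: "In a clinical trial, the study product must always be suspect". Three levels follow.

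- *Definitely Related* opens with "There is clear evidence to suggest a causal relationship, and other possible contributing factors can be ruled out" and continues with "The clinical event occurs in a plausible time relationship to study capsule administration and cannot be explained by concurrent disease, medications, or other treatments".
- The middle level, *Probably Related*, asks for evidence of causality with other factors unlikely, and an event within a reasonable time after the capsule.
- *Not Related* reads: "The AE is completely independent of study capsule administration, and/or evidence exists that the event is definitely related to another etiology". The clinician must also document the definitive alternative cause.

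Table 1 (Investigator AE Reporting Requirements) has a row for "Device Related AE/SAE", due to the sponsor within 24 hours. The general AE row allows 10 working days. The protocol does not say which causality levels put an event in the device-related row.

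The Unanticipated Problems (UP) Definition uses the phrase "Related or possibly related to participation in the research" and explains the second term there as a reasonable possibility of causation.

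**The concern.** A causality scale has to name the product actually given and provide a level for every event it may meet. This one does neither. The capsule reference looks like wording carried over from another template. The missing middle level matters more, because it remains after the wording is corrected.

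The gap is likely to be met in practice. The events that the protocol lists as feasible with the device are skin irritation, discoloring, rash, indentations and infection, and several of these can easily have other causes. The study has a single arm, so no control group shows the background rate of such events. The investigator's judgment is the only thing that separates a device event from a coincidental one. If the scale offers no honest answer for a mixed case, two investigators can grade the same rash differently and neither will have followed the definitions.

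The grade also has an operational use, since Table 1 sets a different sponsor deadline for device-related events.

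**Working it through.** There is no planned figure to reproduce and no arithmetic applies. The check compares the definitions with the intervention, with one another and with the places that use the grade.

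**Step 1: the named product.** The treatment section describes eight laser sessions. Each of the three causality definitions refers to a capsule. The error is therefore in the whole scale, not in one line.

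**Step 2: is the scale complete once capsule is read as GVS treatment?** Take a rash that appears soon after a session, in a subject for whom another cause (an assumed example is contact irritation) is about as plausible as the laser.

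| Level | What the definition requires | Does the rash meet it? |
|---|---|---|
| Definitely Related | Clear evidence; other factors ruled out | No: the other cause is not ruled out |
| Probably Related | Evidence of causality; other factors unlikely | No: the other cause is not unlikely |
| Not Related, first limb | Complete independence from the treatment | No: the laser remains plausible |
| Not Related, second limb | Evidence of a definite other cause, documented | No: the other cause is plausible, not definite |

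The rash meets no level. The lead-in still requires a grade from this list, and the list has no possible, unknown or not-assessable option.

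**Step 3: where the grade is used.** In Table 1 a serious event goes to the sponsor within 24 hours whether or not it is related, so the gap does not change the sponsor deadline for serious events. For a non-serious event, the sponsor deadline is 24 hours if it is device related and 10 working days otherwise. The rash has no valid grade, and the protocol does not map grades to the device-related row, so its deadline is undetermined.

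**Step 4: where the grade is not used.** Under Adverse Event Recording, all AEs are documented regardless of relationship. Safety Analyses says only that observed or reported AEs will be evaluated and specifies no table by relationship. The primary endpoint rests on blinded identification of photographs and does not use AE grades.

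**The case against.** The strongest reply is that the protocol's intent is clear and protects against under-attribution. Part B is headed and introduced by reference to the study intervention, and other safety sections speak of the study procedure or study product. No investigator is likely to be misled by the word capsule. The study product is always to be suspected, and Not Related calls for a documented definitive alternative. All AEs are recorded whatever the grade.

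Much of this stands, and it rules out three stronger readings that a reader might infer.

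- *Every event is Not Related because no capsule exists.* The literal words of the first limb of Not Related would allow this. The heading, the lead-in, the instruction to suspect the product and the documentation requirement all point the other way. Nor does the protocol direct that uncertain events be graded Not Related.
- *The scale contradicts the unanticipated-problem definition.* That definition explains its own term, concerns participation in the research and does not refer to the AE scale. It can be applied without a matching AE level.
- *The gap biases a device-related AE rate by a known amount.* The plan defines no such rate and gives no expected event counts. Any percentage would rest on invented events.

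What the reply does not answer is Step 2 of the working. The safeguards tell the investigator that the uncertain rash is not Not Related, but they do not make it Probably or Definitely Related. They exclude one level without supplying another.

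**Conclusion.** The point holds as a defect in the safety classification. The product is misnamed in all three definitions. After the obvious correction, the scale still has no level for an event with plausible device and non-device causes, although every AE must be graded on it.

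The consequences are limited. Attribution of uncertain events will be inconsistent, in either direction, and the sponsor deadline for a non-serious event of this kind is unclear (24 hours or 10 working days). Any summary of AEs by relationship would inherit the inconsistency, though none is specified. No size in events or percentage points can be derived from the documents.

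The conclusion assumes that the AE case report form does not already carry a further level. The forms are not in the text available, so this could not be checked. If they do carry one, the protocol definitions should be brought into line with them.

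**What to change.** Four changes to the protocol, best made before AE data are collected so that events need not be re-graded afterwards by unblinded investigators:

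1. Replace the capsule wording with GVS treatment in all three causality definitions.
2. Add a *Possibly Related* level for an event with a plausible time relationship to GVS treatment where another cause is also plausible. Use the reasonable-possibility meaning that the protocol already gives under the Unanticipated Problems (UP) Definition.
3. State which levels count as device related for the 24-hour row of Table 1 and for any summary of AEs by relationship.
4. Align the AE case report form if it does not already offer this level.

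The cost is an amendment to wording and, if needed, one option on a form. The downside is that slightly more events may be reported as device related. Sample size, visits and the primary analysis do not change.

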5. Subject-Reported perception of Skin Tightness at 4 and 12 weeks post-final treatment.

Subject-Reported perception of Skin Tightness outcome ratings recorded at each of 4 and 12 weeks post-final treatment will be assessed and compared.

COVARIATE/SUBGROUP ANALYSIS

The impact of the following potential covariates on the primary study efficacy outcome may be evaluated, as indicated:

- Age
- Gender
- Ethnicity
- Race
- Baseline height (m)
- Baseline body weight (kg)
- Baseline BMI (kg/m^2)
- Baseline waist circumference measurement (in)
- Baseline hips circumference measurement (in)

ADDITIONAL CONSIDERATIONS

Depending on the variations identified, a discussion on the potential impact of variability in subject reported use of medications and procedures, and diet and exercise patterns at baseline assessment may occur.

SAFETY ANALYSES

Safety will be assessed by evaluating observed and/or reported adverse events.

ADVERSE EVENTS

At each evaluation and measurement point throughout the clinical study, and at any other time throughout the duration of the clinical trial that is necessary, all potential adverse events reported by a subject or observed by an investigator will be recorded on the case report form, and subsequently evaluated by the investigator for its relation to the study procedure and whether any corrective action needs to be taken. All potential adverse events recorded will be appropriately reported to the governing IRB, as applicable.

It is unlikely and not expected that any adverse events will result from implementation of this clinical study protocol. Prior clinical trials using low level laser light, including the prior Erchonia clinical study evaluating the Erchonia green and violet laser combination, have not typically yielded any adverse events or reactions. However, potential adverse events that may feasibly occur from application of the Erchonia® GVS include, but are not necessarily limited to skin irritation, discoloring, rash, indentations, and infection.

ADVERSE EVENTS DEFINITION

An adverse event means any untoward medical occurrence associated with the use of an intervention in humans, whether or not considered intervention-related (21 CFR 312.32 (a)).

SERIOUS ADVERSE EVENTS (SAE) DEFINITION

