A protocol deviation is any noncompliance with the clinical trial protocol, ICH GCP, or Manual of Procedures (MOP) requirements. The noncompliance may be either on the part of the subject, the investigator, or the study site staff. As a result of deviations, corrective actions are to be developed by the site and implemented promptly.

These practices are consistent with ICH GCP:

- 4.5 Compliance with Protocol, sections 4.5.1, 4.5.2, and 4.5.3
- 5.1 Quality Assurance and Quality Control, section 5.1.1
- 5.20 Noncompliance, sections 5.20.1, and 5.20.2.

It is the responsibility of the site investigator to use continuous vigilance to identify and report deviations within 5 working days of identification of the protocol deviation, or within 5 working days of the scheduled protocol-required activity. All deviations must be addressed in study source documents (CRFs) and be reported to the sponsor. Protocol deviations must be sent to the reviewing IRB as applicable per their policies. The site investigator is responsible for knowing and adhering to the reviewing IRB requirements.

The investigator will not intentionally deviate from the study protocol procedures except in medical emergencies. Any and all protocol deviations that do occur will be recorded on the CRF and the IRB will be informed of the deviation, if applicable.

Protocol deviations will be recorded in CRFs and monitored for completion and accuracy during each monitoring visit.

SUBJECT SAFETY MONITORING

Subject safety data will be recorded in CRFs and monitored for completion and accuracy during each monitoring visit.

Subjects will be asked about any adverse events at the test site and are required to record any

potential adverse events in the Adverse Events Record Form and to notify the test site immediately. In such an occurrence, an unscheduled visit may be arranged so that the Investigator can clinically evaluate the findings. All adverse events will be recorded and reported as per the plan described in the relevant section above.

The Investigator can decide to stop the subject's participation in the study if he/she believes that subjects' participation is no longer safe.

The sponsor or the IRB may stop the research for the safety of the subjects if unreasonable risks to subjects persist.

PROTOCOL AMENDMENTS

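### The protocol text requires adverse events to be split into solicited and unsolicited, but describes no question that could produce a solicited event and lists no field to record the split

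*Combined protocol and SAP*

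**What the plan says.** The section on time period and frequency for event assessment and follow-up sets two definitions and one requirement. An unsolicited event "is defined as one that is reported without specific prompting or in response to a general question". A solicited event "is one that is specifically solicited through asking a question regarding a specific potential AE". The requirement follows: "Reporting and data collection for an AE will distinguish if a captured AE was unsolicited or solicited".

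The next section, on reasonably anticipated and potential adverse events, states that the feasible events "include, but are not necessarily limited to skin irritation, discoloring, rash, indentations, or infection". The Adverse Events section under Safety Analyses names the same five.

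The text describes these ways of capturing an event:

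- Subject Safety Monitoring: "Subjects will be asked about any adverse events at the test site". The same sentence obliges subjects to enter potential events on an Adverse Events Record Form and to tell the site at once.
- Adverse Events (Safety Analyses): "all potential adverse events reported by a subject or observed by an investigator will be recorded on the case report form", at every evaluation point and at other times as needed.
- Treatment Administration Record: after each session the investigator notes an adverse event where there is one. No reactions are listed.
- The 4-week and 12-week evaluations: each lists an adverse events assessment, with no description of its content.

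Adverse Event Recording lists what the form collects: description, onset, severity, relationship, action taken, resolution and any withdrawal. Safety Analyses adds only that observed and reported events will be evaluated.

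**The concern.** A plan that separates solicited from unsolicited events normally says which events will be asked about by name, and when. Here the natural candidates are the five reactions that the plan itself names, yet no section says that subjects will be asked about any of them. The described enquiry falls, by the plan's own definition, on the unsolicited side.

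What is at stake is how the safety result of this study can be read. A general question tends to miss mild or short-lived effects such as passing irritation, particularly between visits. The study is single-arm and open-label, and the protocol tells sites that adverse events are improbable. With 35 subjects, a count of zero or one is easily over-read as evidence of tolerability when it may partly reflect how the question was put. The primary endpoint and the sample size are not affected.

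**Working it through.** The plan gives no safety figure to reproduce. The main check sets each described route against the definitions.

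| Route | Section | Class under the plan's definitions |
|---|---|---|
| Enquiry to subjects about any event | Subject Safety Monitoring | Unsolicited (general question) |
| Subject's own record form | Subject Safety Monitoring | No specific prompt described; unsolicited as described |
| Investigator observation | Adverse Events | No question is asked, so not solicited |
| Entry after each session | Treatment Administration Record | No specific prompt described; unsolicited as described |
| Assessments at 4 and 12 weeks | The two evaluation sections | Content not described; cannot be classed |

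No row describes a question about a named reaction. The list of form fields contains no item for the split, although that list is introduced as what is included and need not be complete. The safety analysis does not mention the split or give a denominator for reporting it.

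The second check shows how much capture could matter. It is an illustration.

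Inputs: N = 35 enrolled (Sample Size; the safety population is all enrolled subjects). Assumed, because the documents give no value: s, the probability that an affected subject is recorded, and p, the true proportion of subjects affected.

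1. Zero recorded events with full capture. The one-sided 95% upper limit is 1 − 0.05^(1/35) = 0.0820, or 8.2%.
2. With partial capture, the recorded proportion is p × s, so the limit on p is 0.0820 / s:
   - s = 0.75: 0.0820 / 0.75 = 10.9%
   - s = 0.50: 0.0820 / 0.50 = 16.4%
   - s = 0.25: 0.0820 / 0.25 = 32.8%
3. The chance of recording at least one case is 1 − (1 − p × s)^35:

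| True rate p (assumed) | s = 1.00 | s = 0.75 | s = 0.50 | s = 0.25 |
|---|---|---|---|---|
| 2% | 50.7% | 41.1% | 29.7% | 16.1% |
| 5% | 83.4% | 73.8% | 58.8% | 35.6% |
| 10% | 97.5% | 93.5% | 83.4% | 58.8% |

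The first check rests only on the text. The second shows that the reading of a low count depends heavily on s, which the plan neither states nor controls.

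**The case against.** The strongest reply is that the wording of questions belongs in the case report forms, which are an appendix not available for this review. The adverse event form, the subject's record form and the content of the 4-week and 12-week assessments are all unseen, and any of them may carry specific prompts. The sentence in Subject Safety Monitoring states a duty to ask and is not a script. This stands. A reader might infer that the five reactions are never asked about, or that the solicited category will be empty. The documents do not support either inference; they show only that the protocol text describes no such question.

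A second reply is that events do not depend on subjects volunteering them. Investigators record what they observe, the treated abdomen is under the device at eight sessions and photographed at three time points, and discoloring, rash and indentations can be seen. Subjects also keep their own record. This stands too, and limits the likely under-recording to milder reactions that are not visible at a visit. These routes do not, as described, produce solicited data.

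Third, the protocol does tell sites which reactions are feasible, directly after saying that events are improbable. That is fair, but telling sites what may occur is not the same as asking subjects about it.

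Fourth, the capture rates are assumed. They are, and 50% takes no account of observation or the subject's own record.

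Finally, an empty category would not in itself breach the requirement, which asks only that each captured event be classed. That is correct, but the listed fields still show no place to record the class.

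**Conclusion.** The point holds as a gap in the protocol text. It requires a distinction, describes no procedure that generates one side of it, and lists no field to record it. The reactions that the plan names as feasible are left to general enquiry, self-record and observation.

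The size of any under-recording is unknown. If no events are recorded in 35 subjects, the upper limit on the true rate is 8.2% with full capture, and about 11% or 16% if 75% or 50% of events are captured; 25% capture would give about 33%. These capture values are assumptions.

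A reader might go further and conclude that the safety result is biased towards zero, or that it is the only tolerability evidence for the submission. The first is not shown, because the forms are unseen and investigator observation is in place. The second is not supported, because the Adverse Events section refers to an earlier study of the sponsor's green and violet laser combination, and the contents of the submission are not given.

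This is a worthwhile and inexpensive improvement to safety data collection. If the forms already contain the prompts and the field, only a cross-reference and matching protocol wording remain to be done.

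**What to change.** First, check the case report forms. Unless they already do this:

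1. Add a short yes/no checklist of the five named reactions, with the plan's severity grade for each yes, to the session record and to the treatment-end and 12-week adverse event assessments. Keep the general question alongside it.
2. Add a solicited/unsolicited field to the adverse event form, and include it among the fields listed in Adverse Event Recording.
3. In Safety Analyses, report each solicited reaction as subjects affected out of subjects treated, and report unsolicited events separately.
4. Align Treatment Administration Record, the time period and frequency section, Adverse Event Recording and Subject Safety Monitoring, so that they describe the same enquiry. Correct the cross-reference to the forms as well: the list of appendices places them in Appendix E, while the Case Report Forms section points to Appendix D.

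The cost is about half a page of form and one table. The checklist is used at most ten times per subject (eight sessions plus two evaluations), all at existing contacts. The endpoint, sample size and treatment are unchanged. The downside is that the reported adverse event rate may be slightly higher.
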